#### 10.4 Efficacy of Octafibrin in all Bleeding Episodes

The same analyses as described for the first bleeding episode will be done for the total number of bleeding episodes.

Haemostatic efficacy will be displayed by covariates (sex, age groups, weight, and type of bleeding) in tables or with covariates in listings depending on the number of bleeding episodes per subgroup.

The following will be presented following the manners of presentation described in section 7:

- Type of bleeding episodes (spontaneous, traumatic, post-operative, other)
- Site of bleeding episodes
- duration of bleeding episodes

If the end time of a bleeding episode is missing it will be set to 23:59 of the same day, if the start time of a bleeding episode is missing it will be set to 0:00 of the same day.

- Severity of bleeding episodes (mild, moderate, severe)
- Efficacy assessment of the treatment of a bleeding episode made by the investigator (excellent, good, moderate, none)

In the following situations the haemostatic efficacy outcome will be set to the worst efficacy category, i.e., 'none':

- Subjects who withdraw from the study due to lack of efficacy: all bleeding episodes of that subject
- Subjects receiving cryoprecipitate or concentrates containing fibrinogen other than the IMP between first infusion and efficacy assessment (unless it is clearly documented that these products were administered for reasons unrelated to IMP efficacy [e.g., pharmacy error]): the actual bleeding episode
- Subjects with missing haemostatic efficacy assessment: the actual bleeding episode
- In addition to the four point scale the proportion of bleeding episodes successfully treated with *Octafibrin* will be evaluated. "Successfully treated" are all "excellent" and "good" efficacy ratings of treated bleeding episodes. A two-sided 95% CI for the success rate in haemostatic efficacy ('excellent' or 'good') according to Clopper/Pearson will be computed.
- The final efficacy assessment of each patient will be adjudicated by an Independent Data Monitoring & Endpoint Adjudication Committee (IDMEAC). The results of the adjudication will be shown together with the assessments of the investigator.

- Treatment details: number of exposure days, number of injections, dosing incl. batch numbers., consumption of *Octafibrin* (IU/kg per month, per year, per bleeding episode) will be listed
- Increase and decrease of doses of *Octafibrin* used to treat individual bleeding episodes will be listed.
- Any haemostatic co-medication will be listed.

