### **Haemostatic efficacy in the treatment of all bleeding episodes**

In addition to the 'first BE per patient approach' (primary endpoint), success rates will be presented with two-sided 95% confidence intervals for all documented bleeding episodes, both considering each bleeding episode as an independent case within each subject and considering outcomes of assessments as repeated measurements within the same patient, if applicable (e.g., by general estimation equations with intra-subject correlation structure).

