### 9.3.2.2 *Clot strength (MCF)*

The analysis of MCF will be provided for the BLEED population.

MCF before as well as MCF and fibrinogen activity 1 hour after the end of the first infusion, as well as changes in MCF from pre-infusion will be summarised over all bleeding episodes using descriptive statistics. The course of laboratory data will be presented graphically. Mean changes in MCF will be described with 2-sided 95% CIs based on the paired t-test.

The same analyses or respective listings (depending on the number of observations per subgroup) will be provided separated for the predefined subgroups as well as separated for the subjects' clinical outcome represented by each step of the 4-point haemostatic efficacy scale (excellent, good, moderate, none) and the dichotomised haemostatic efficacy scale (excellent/good, moderate/none). Boxplots will show MCF by haemostatic efficacy outcome, if applicable.

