#### **9.3.2.4 Efficacy of *Octafibrin* in All Bleeding Episodes**

The efficacy of *Octafibrin* in the treatment of all bleeding episodes recorded throughout the study observation period will be assessed in the same way as the efficacy of *Octafibrin* in the treatment of the first bleeding episode per patient (see Section 9.3.1).

In addition to the ‘first BE per patient approach,’ haemostatic efficacy (4-point scale) and success rates for the treatment of bleeding episodes will be presented descriptively for all bleeding episodes (BLEED population) by frequency tables.

Success rate estimates will also be provided with two-sided 95% CIs, considering both

- the assessments of each bleeding episode as an independent case within each subject and
- outcomes of assessments as repeated measurements within the same patient, if applicable (e.g., by general estimation equations with intra-subject correlation structure).

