## 2 PURPOSE

This Statistical Analysis Plan describes all statistical analyses to be performed on data collected in study FORMA-04 in full detail, and the resulting output that will be compiled for the integrated clinical study report.

No inferential statistics but only explorative and descriptive statistics are planned for this uncontrolled trial.

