Although all bleeding episodes occurring throughout the study observation period will be documented, only the first bleeding episode per patient will be used for the analysis of the primary endpoint. This is because the study will end once the 6th enrolled patient (i.e., at least 3 patients in each of the specified age groups) has at least one documented bleeding episode, potentially resulting in a large diversity in the number of bleeding episodes between patients; also, the haemostatic outcomes in different bleeding episodes within one patient cannot be regarded as independent/uncorrelated. The entirety of bleeding episodes documented in the study will be assessed as a secondary endpoint.

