### 10.2 Clot strength (MCF)

MCF and fibrinogen activity will be measured for each bleeding episode, once pre-infusion and once 1 hour after the first infusion. The analysis of MCF will be provided for the BLEED population.

The following will be presented following the manners of presentation described in section 7:

- Descriptive statistics of MCF and fibrinogen activity before and 1 hour after the end of the first infusion over all bleeding episodes, as well as changes between the two time points will be presented, together with 2-sided 95% CIs based on the paired t-test for the difference.
- If the number of bleedings is appropriate an analysis as described before will be provided separated by the 4-point haemostatic efficacy scale (excellent, good, moderate, none) and/or a dichotomised haemostatic efficacy scale (excellent/good, moderate/none). Otherwise listings with the patient data for MCF and fibrinogen activity will be given.
- If the number of bleedings is appropriate box plots will be provided separated by the 4-point haemostatic efficacy scale and/or the dichotomised haemostatic efficacy scale for MCF and fibrinogen activity.

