14.2.3	T	Frequency of bleeding episodes per age group and in total	BLEED, BLEED-PP (age groups)
14.2.4	T	First bleeding episode per type of BE (spontaneous, traumatic, post-operative, other)	BLEED, BLEED-PP
14.2.5	T	Bleeding episodes per type of BE (spontaneous, traumatic, post-operative, other)	BLEED, BLEED-PP
14.2.6	T	Site of first bleeding episode	BLEED, BLEED-PP
14.2.7	T	Site of bleeding episodes	BLEED, BLEED-PP
14.2.8	T	Treatment duration of the first bleeding episode	BLEED, BLEED-PP
14.2.9	T	Treatment duration of bleeding episodes	BLEED, BLEED-PP
14.2.10	T	Severity of first bleeding episode (mild, moderate, severe)	BLEED, BLEED-PP
14.2.11	T	Severity of bleeding episodes (mild, moderate, severe)	BLEED, BLEED-PP
14.2.12	T	Efficacy assessment (final outcome) of treatment of first bleeding episode a) Four point scale (14.2.11.1) (excellent, good, moderate, none) b) Two point scale (successfully treated (excellent or good), not successfully treated (moderate or none) (14.2.11.2))	BLEED, BLEED-PP (age groups)
14.2.13	T	Statistics on successfully treated first bleeding episodes (two-sided 95% Clopper-Pearson confidence interval)	BLEED, BLEED-PP
14.2.14	T	Efficacy assessment (final outcome) of treatment of bleeding episodes a) Four point scale (14.2.13.1) (excellent, good, moderate, none) b) Two point scale (successfully treated (excellent or good), not successfully treated (moderate or none) (14.2.13.2))	BLEED, BLEED-PP (age groups)
14.2.15	L	Treatment details for each bleeding episode per patient (incl. exposure days, number of injections, dosing inc. batch numbers, consumption of Octafibrin, haemostatic co-medication)	BLEED, BLEED-PP
14.2.16	T	Statistics on successfully treated bleeding episodes (two-sided 95% Clopper-Pearson confidence interval)	BLEED, BLEED-PP
14.2.17	T	Statistics on MCF and fibrinogen activity for samples taken before and 1 hour after the end of the first infusion (including confidence interval for the difference)	BLEED, BLEED-PP
14.2.18	T	Statistics on MCF and fibrinogen activity for samples taken before and 1 hour after the end of the first infusion separated by four/two point efficacy scale	BLEED, BLEED-PP
14.2.19	F	Boxplot MCF and fibrinogen activity for samples taken before and 1 hour after the end of the first infusion separated by four/two point efficacy scale	BLEED, BLEED-PP
14.2.20	T	Statistics on final efficacy assessment of the IDMEAC and the efficacy assessment of the investigator	BLEED, BLEED-PP

		Surgeries	

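### The SAP omits the protocol's within-patient confidence interval for the all-episode success rate; separately, the paired-t intervals for clot firmness and fibrinogen activity ignore repeat bleeds in one child

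*SAP*

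**What the plan says.** **All-episode success rate.** Protocol 9.3.2.4 and the protocol outline plan two-sided 95% CIs under two approaches. The outline describes them as "both considering each bleeding episode as an independent case within each subject and considering outcomes of assessments as repeated measurements within the same patient". Section 9.3.2.4 words the second as "outcomes of assessments as repeated measurements within the same patient, if applicable (e.g., by general estimation equations with intra-subject correlation structure". It is therefore conditional, and GEE is only an example.

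SAP 10.4 opens with "The same analyses as described for the first bleeding episode will be done for the total number of bleeding episodes" and specifies a Clopper-Pearson interval. The matching output, Table 14.2.16, is titled "Statistics on successfully treated bleeding episodes (two-sided 95% Clopper-Pearson confidence interval"). No repeated-measures method appears anywhere in the SAP, and no statement says that one was judged inapplicable. SAP section 2 nevertheless gives its scope as: "This Statistical Analysis Plan describes all statistical analyses to be performed on data collected in study FORMA-04 in full detail". Sections 3 and 5.1 both say that "the haemostatic outcomes in different bleeding episodes within one patient cannot be regarded as independent/uncorrelated".

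**Clot firmness (MCF).** Protocol 9.3.2.2 states: "Mean changes in MCF will be described with 2-sided 95% CIs based on the paired t-test". SAP 10.2 summarises MCF and fibrinogen activity before and 1 hour after the first infusion over all episodes, with the changes, "together with 2-sided 95% CIs based on the paired t-test for the difference". Table 14.2.17 covers both variables. The analysis set is BLEED, which is a set of episodes, not of children.

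**The concern.** Repeat episodes per child are allowed with no stated maximum, as many as possible are to be documented, and the SAP expects the number per child to vary widely. The one all-episode interval it keeps rests on the independence that it says cannot be assumed. Table 14.2.16 could then show precision that comes from repeat bleeds in a few children. If every episode succeeds, the Clopper-Pearson lower limit rises from 54.1% at 6/6 to 73.5% at 12/12 and 85.8% at 24/24, without one more child being studied.

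The MCF issue has the same cause but a different status. A paired t interval handles the before/after pairing within an episode. It does not handle several episodes from one child. Here the two documents agree, so this is a weakness of the chosen analysis and not a discrepancy.

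**Working it through.** **Text check.** Set side by side, the protocol has two intervals and the SAP has one. SAP section 7 makes analyses conditional on patient numbers, but only those the SAP describes, and the within-patient interval is not among them.

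**Inputs.** From the documents: at least 6 children with a bleeding outcome (protocol 9.1, SAP 5.3), at least 12 enrolled, 95% two-sided intervals. Neither document states a sample-size calculation or expected interval, so there is no plan figure to reproduce. Assumed, because the documents give none: ICC ρ = 0.3; true success rate p from 0.70 to 0.95; bleeds per child of 2 each, 4 each, or 1, 1, 2, 3, 5, 12. The last is deliberately extreme, with half of all bleeds in one child. For 12 children each pattern is repeated twice.

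**Lower limit when all n episodes succeed:** 0.025^(1/n). This gives 54.1% (n = 6), 73.5% (n = 12) and 85.8% (n = 24).

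**Effective number of episodes:** design effect = 1 + (Σm²/Σm − 1)ρ, with m the bleeds per child.

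- 2 each: 1 + (24/12 − 1)(0.3) = 1.3, so 12 episodes act like 12/1.3 = 9.2.
- 4 each: 1 + (96/24 − 1)(0.3) = 1.9, so 24 act like 12.6.
- Uneven: 1 + (184/24 − 1)(0.3) = 3.0, so 24 act like 8.0.

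**Clopper-Pearson coverage.** Each child's success probability is drawn from Beta(a, b) with a = p(1 − ρ)/ρ and b = (1 − p)(1 − ρ)/ρ. Coverage at p is the probability that the limits from the pooled count contain p. It was evaluated for p = 0.70 to 0.95 in steps of 0.01, because coverage moves sharply between neighbouring rates and a few selected rates miss the low points.

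**Paired-t coverage.** Normal random child effect with share ρ of the variance, 40,000 runs, compared with a t interval on child means with (children − 1) df.

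| At ρ = 0.3 | 2 each | 4 each | Uneven |
|---|---|---|---|
| Clopper-Pearson, 6 children, minimum over p | 92% | 85% | 74% |
| Clopper-Pearson, 6 children, maximum over p | 99% | 96% | 94% |
| Clopper-Pearson, 12 children, minimum over p | 92% | 85% | 74% |
| Paired-t change, 6 children | 91% | 84% | 73% |
| Child-mean t, 6 children | 95% | 95% | 95% |

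All entries are approximate. Minimum coverage does not improve with 12 children, because the relative weight of repeat bleeds is the same. Over ρ = 0.1 to 0.5 the child-mean t interval is 1.1 to 2.3 times as wide as the paired-t interval.

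**The case against.** The strongest reply to the first part is that the protocol's interval is conditional, that GEE is only illustrative, and that the SAP never withdraws it. That stands as far as it goes. A reader might infer that the SAP contradicts the protocol or breaks a commitment to GEE, and the text supports neither. But a conditional analysis needs a condition. Protocol section 9 assigns the details of all analyses to the SAP, and the SAP is silent.

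Second, the restored interval may be unhelpful with few children. This is fair. With 6 children, ρ = 0.3 and a true rate of 0.95, all episodes share one outcome in about 45–60% of simulated trials (19–34% at 0.90), and GEE then cannot be fitted. When it can, a small-sample correction (Mancl-DeRouen, t with 5 df) is conservative: at 23/24 with 4 bleeds each, the lower limit is 54.9% against 78.9% for Clopper-Pearson. This argues for a stated fallback, not for omitting the interval.

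Third, clustering stays visible: Table 14.2.2 shows bleeds per child, listing 16.2.6.1 shows outcomes per episode, and Table 14.2.13 gives a first-bleed interval with one episode per child. This stands and limits the consequence, though none of these is an all-episode interval that allows for clustering.

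Fourth, for MCF the child-mean interval weights children and not episodes, so it answers a slightly different question. That also stands. It belongs beside the planned interval, not in its place.

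**Conclusion.** The first part holds: a conditional but planned interval is missing from the SAP without explanation, and the one retained assumes what the SAP itself denies. Under the assumptions above, its worst-case coverage is about 92%, 85% and 74% for the three patterns. The lowest figure depends on a deliberately extreme pattern, and coverage is higher at many true rates. If no child rebleeds, nothing changes.

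The second part holds as a separate analysis weakness, affecting MCF change (both documents) and fibrinogen activity change (SAP only). Coverage is about 91%, 84% and 73% under the same patterns.

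A reader might go further and infer that the primary result is compromised or that an error rate is inflated. The documents do not support this. The primary endpoint uses one first episode per child, no confirmatory test is planned, and all analyses are descriptive. Nor do the documents show that the intervals will in fact be too narrow, since that depends on bleed counts and a correlation they do not give. This is a change that should be made, to secondary intervals only.

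**What to change.** **Success rate (SAP 10.4, Table 14.2.16).** Keep Clopper-Pearson and label it as assuming independent episodes. Beside it, report the protocol's within-patient 95% CI whenever any child has more than one treated bleed; otherwise state that it is not applicable. Before database lock, name one small-sample clustered method and say what is reported when it cannot be fitted, for example at 0% or 100% success. Referring to the first-bleed Clopper-Pearson interval in Table 14.2.13 would serve. A sensitivity display over several assumed ICC values is optional.

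**Clot firmness and fibrinogen activity (SAP 10.2, Table 14.2.17).** Keep the planned paired-t intervals, labelled as ignoring repeat bleeds in one child. Add a t interval on child-mean changes (df = children − 1) for both variables, stating that it weights children rather than episodes and is wider.

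**Cost.** SAP wording and some extra output lines. No planned analysis is removed or changed. The price is wider, less favourable intervals, and with 6 children the within-patient success interval may be very wide; the SAP should say so.

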## 10.5 Surgical Prophylaxis

Efficacy of *Octafibrin* in surgical prophylaxis will be assessed intra-operatively (at the end of surgery = after last suture) by the surgeon and post-operatively (at the last post-operative day) by the haematologist using two 4-point efficacy scales.

The primary analysis regarding haemostatic efficacy will be done on the adjudicated assessments by the algorithm described above and by the IDMEAC.

The following will be presented in frequency tables with descriptive statistics or in listings, depending on the number of surgeries:

- Number of subjects undergoing surgeries (minor, major, total)
- Number of surgeries, overall (minor, major, total)
- Surgery characteristics (type and site, pre-planned (yes/no), severity, expected and actual duration, expected and actual blood loss) will be listed.
- Details on treatment for surgical prophylaxis (number of exposure days and injections prior to surgery, dosing details, total amount of *Octafibrin*) will be listed.
- Pre-, intra-, and post-operative fibrinogen plasma levels, pre- and post-infusion will be listed.
- Efficacy evaluation by the surgeon at the end of the surgery and by the haematologist on the last post-operative day.
- Subjects who switch to another FIX product during a surgery will be considered treatment failures, i.e. the efficacy will be imputed to be “none” for each haemostatic efficacy assessment after the switch in the efficacy analyses for this surgery.
- Adjudicated overall efficacy assessment of the surgeries using the algorithm for the adjudicated intra- and post-operative assessments of haemostatic efficacy (as described in chapter 3.3.6 of this SAP). All assessments adjudicated by the IDMEAC will be listed together with the surgery details and the intra- and post-operative assessments of the surgeon and the haematologist.

## 11 EVALUATION OF PHARMACOKINETICS

The primary analysis will be based on the PK-PP population.

The exact applied dose of fibrinogen concentrate (expressed as mg/kg dosed) will be calculated for each subject, based upon the actually administered amount of study treatment (planned: single intravenous infusion of 70 mg/kg body weight of *Octafibrin*) and the potency of fibrinogen in the actually used batch.

The pharmacokinetic parameters will be determined from plasma fibrinogen levels taken before and at 1 hour and 3 hours after injection, as well as on days 2, 5, 7, 10 and 14.

For the additional recovery assessments blood samples for the calculation of the incremental recovery will be taken prior to the study drug injection, 1 hour and 3 hours post-infusion.

PK analysis on fibrinogen activity and antigen levels will be performed per patient with a non-compartmental model using standard PK software (Phoenix WinNonlin, Version 6.3 or higher [1]); this includes graphical displays of individual elimination curves. Individual endogenous baseline concentrations, if any, will be taken into account by subtraction from post-baseline values. The resulting PK parameters (i.e., area under the concentration-time curve (AUC), incremental IVR, classical IVR, terminal elimination half-life ( $t_{1/2}$ ), maximum plasma concentration ( $C_{max}$ ), time to reach maximum plasma concentration ( $T_{max}$ ), mean residence time (MRT), volume of distribution ( $V_{ss}$ ), and clearance (Cl)) will be summarized and presented as described for continuous variables in section 6.

Fibrinogen plasma levels below the limit of quantification will be set to 0 for PK calculations.

The following pharmacokinetic parameters will be estimated by non-compartmental analysis:

$C_{max}$	Peak concentration observed	until the end of the 14 days PK period
$C_{max,norm}$	Observed peak concentration normalised for the dose given	$C_{max,norm} = \frac{C_{max}}{D}$ 
where D is the dose in IU administered according to the actual potency of Octafibrina

$T_{max}$	Time when $C_{max}$ is observed	Timing starts at end of injection
$T_{1/2}$	Elimination half-life	
using linear regression on the terminal phaseb of the logarithm of the concentration;
 $T_{1/2} = \frac{\ln(2)}{K}$

a The actual dose D based on the real potency of the batch of medication used will be calculated as  $D = D_{nom} \times$  Actual Potency/Labelled Potency where  $D_{nom}$  stands for the nominal Dose according to the product label. For the determination of PK properties of *Octafibrin* this actual dose will be used.

b The non-compartmental approach does not presume that the plasma concentration follows a mono-exponential decay during the complete elimination phase ( $t \geq T_{max}$ ). The appropriate time point when the terminal elimination phase starts will be determined automatically by the Software WinNonlin using the algorithm described in Appendix I: Determination of slope of elimination by non-compartmental PK analysis with WinNonlin® [1, Chapter 9, pages 218-219]. In addition visual examinations on the choice of the software will be performed on individual plots of the natural logarithm of the plasma levels  $\ln(C)$  against time to determine whether linear regression yields a good approximation for  $\ln(C)$  obtained at times  $t \geq T_{max}$ , or whether it's more appropriate to assume a terminal elimination phase that starts later ( $t \geq T_E, T_E \geq T_{max}$ ).

		(where $K$ , the elimination rate constant, is determined as the slope of the regression line)
$AUC_{last}$	Area under the curve from time point $t=0$ a (i.e. the end of drug injection) to the last measured value	using the linear trapezoidal rule $AUC_{last} = \sum \frac{(C_n + C_{n+1})}{2} \cdot \Delta t$
$AUC$	Area under the curve from baseline to infinity	$AUC = \sum \frac{(C_n + C_{n+1})}{2} \cdot \Delta t + \frac{C_{last}}{K}$ ( $C_{last}$ is the last available measurement)
$AUC_{norm}$	$AUC$ normalised with respect to the dose administered	$AUC_{norm} = \frac{AUC}{D}$ where $D$ is the dose in IU administered according to the actual potency of Octafibrin as described in a .
$AUMC$	Area under the moment curve (from baseline to infinity)	$AUMC = \sum \frac{(t_n \cdot C_n + t_{n+1} \cdot C_{n+1})}{2} \cdot \Delta t + \frac{C_{last} \cdot t_{last}}{K^2}$
$MRT$	Mean residence time	$MRT = \frac{AUMC}{AUC}$
$CL$	Clearance	$CL = \frac{D}{AUC}$ where $D$ is the actual dose administered (see remark a )
$V_{ss}$	Volume of distribution at steady state	$V_{ss} = CL \cdot MRT$

a For the extrapolation of the trapezoidal area under the concentration curve from time point  $t=0$  to the first measured fibrinogen value ( $C_1$ ) the fibrinogen concentration at  $t=0$  ( $C_0$ ) must be estimated. -To account for the presence of fibrinogen in the metabolism already during the infusion but before start of the clock used for the PK calculations ( $t=0$ ), the PK software WinNonlin will automatically perform a log-linear regression of the first two data points to back-extrapolate  $C_0$ . However, in the instance that the regression yields a slope  $\geq 0$ , then the first observed positive concentration (should in this study usually be  $C_1$ ) will be used as an estimate for  $C_0$  [1, Chapter 9, page 234].

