## 1 INTRODUCTION

### 1.1 Background

Human fibrinogen is a plasma glycoprotein synthesised in the liver, and it circulates in the plasma at a concentration of 2.9–4.5 g/L. In healthy human adults, about 2–5 g of fibrinogen is synthesised daily, and the same amount is catabolised [1, 2]. Fibrinogen is essential for haemostasis, wound healing, fibrinolysis, inflammation, angiogenesis, cellular and matrix interactions, and neoplasia. These processes involve the conversion of fibrinogen into fibrin, and often the interaction of fibrinogen with various proteins and cells. The plasma half-life of fibrinogen, under normal physiological conditions, has been estimated to be 3–5 days [3, 4].

The plasma level of clottable fibrinogen may be markedly decreased or even undetectable in various congenital or acquired conditions [5, 6]. Conditions of congenital fibrinogen deficiency include:

- Afibrinogenaemia: Complete absence or extremely low levels of plasma fibrinogen
- Hypofibrinogenaemia: Reduced concentration of plasma fibrinogen
- Dysfibrinogenaemia: Presence of abnormal or dysfunctional fibrinogen molecules

Congenital afibrinogenaemia is a rare inherited autosomal recessive disorder occurring in homozygotic patients with an estimated incidence of 1 in  $10^6$  in the European population [7]. The disease is characterised by a complete lack of coagulable and/or immunologically determinable fibrinogen in the plasma. Patients present with frequent severe bleeding episodes since birth or early childhood [8, 9]. Bleeding may occur after a minor trauma or a small surgical intervention, into the skin, mucosa, muscles, gastrointestinal tract, or the brain.

Congenital hypofibrinogenaemia is more common than afibrinogenaemia and is characterised by low but measurable fibrinogen plasma levels. Clinical symptoms of hypofibrinogenaemia are usually milder compared to afibrinogenaemia, and the condition is frequently combined with a dysfibrinogenaemia that is characterised by an abnormal fibrinogen variant. Several missense mutations in the 3 fibrinogen genes have been identified as the cause of dysfibrinogenaemia and hypofibrinogenaemia that lead to abnormal gene expression resulting in the decreased fibrinogen concentration or dysfunctional fibrinogen molecules.

Therapeutic substitution with human fibrinogen concentrate can correct the haemostatic defect and arrest bleeding in patients with these fibrinogen deficiencies [5, 7, 9, 10, 11].

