#### **PK-Days 2 (24 hrs), 4 (72 hrs), 7 (144 hrs), and 10 (216 hrs)**

- Fibrinogen for PK
- Recording of AEs, including potential thromboembolic events

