## PK-Day 14 (312 hrs)

- Fibrinogen for PK
- Vital signs
- Physical examination, including any signs or symptoms of potential thromboembolic events
- Recording of AEs, including potential thromboembolic events

The flow chart of assessments for the PK phase is provided on page xxiv.

**NOTE:** All adverse events (AEs, see Section 7.4), including thromboembolic events and early signs of allergic or hypersensitivity reactions, occurring between the start of the first *Octafibrin* infusion and the end of the PK phase will be recorded.

All SAEs occurring after the first IMP infusion will be documented and reported for a patient throughout the duration of the patient's participation in the study or as required to meet local regulations.

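### SAP 11 integrates a declining curve with straight lines over gaps of up to 96 h: AUC about 1% to 3% too high and CL too low, with MRT and Vss also affected once the AUMC tail is corrected

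*SAP*

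**What the plan says.** The parameter table in SAP section 11 defines AUC from end of injection to the last sample "using the linear trapezoidal rule", and AUC to infinity as the same sum plus C_last/K. AUMC, described as "Area under the moment curve (from baseline to infinity", is a linear trapezoid of t × C plus a tail printed as C_last × t_last / K². Then MRT = AUMC/AUC, CL = D/AUC and Vss = CL × MRT.

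The logarithm is used in only two places: K comes from a regression on log concentration in the terminal phase, and C0 is back-extrapolated log-linearly from the first two points. A footnote in the same section states: "The non-compartmental approach does not presume that the plasma concentration follows a mono-exponential decay during the complete elimination phase". Values below the limit of quantification are set to 0.

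Protocol 6.1.2 and the PK flow chart place the samples at 1, 3, 24, 72, 144, 216 and 312 h after the end of infusion. SAP 4.3.2 agrees with this (Day 4), but SAP 11 lists sampling "as well as on days 2, 5, 7, 10 and 14". The only half-life in the documents is in Protocol 1.1: under normal physiological conditions it "has been estimated to be 3–5 days".

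**The concern.** An exponential decline is convex, so a chord between two samples lies above the curve and the linear rule adds area on every falling interval. With gaps as long as the half-life, or longer, the excess is not negligible. It is systematic, so averaging over more children does not reduce it. It also grows as the half-life shortens, so a true difference in elimination between the two age groups would carry over into the comparison of AUC and CL.

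AUC, CL, MRT and Vss are named secondary PK endpoints (Protocol 3.1.2.1), and the SAP tabulates them by age group (SAP 7.7; tables 14.2.27, 14.2.30 and 14.2.31). In a descriptive study the point estimates are the result.

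**Working it through.** The documents give no AUC, MRT or Vss value, so there is no planned figure to reproduce. The check applies the SAP formulas to curves whose exact integrals are known.

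**Inputs**
- Times 0, 1, 3, 24, 72, 144, 216, 312 h (Protocol 6.1.2; time 0 by back-extrapolation, SAP 11).
- C0 = 70 mg/kg × 1.77 = 123.9 mg/dL (PK dose and FORMA-01 recovery). This sets the scale only and cancels from percentages.
- Half-life 72 to 120 h (Protocol 1.1, background figure).

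**Formulas**
- Linear: (C1 + C2)/2 × Δt, and the same for t × C.
- Log: with k = ln(C1/C2)/Δt, area = (C1 − C2)/k and moment = (t1·C1 − t2·C2)/k + (C1 − C2)/k².
- Tail: C_last/K for AUC; standard AUMC tail C_last·t_last/K + C_last/K².

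**Half-life 72 h in full.** K = ln 2/72 = 0.009627 per h. Concentrations: 123.9, 122.7, 120.4, 98.3, 62.0, 31.0, 15.5, 6.15 mg/dL.

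| Interval (h) | Linear area | Exact area |
|---|---|---|
| 0–1 | 123.3 | 123.3 |
| 1–3 | 243.1 | 243.1 |
| 3–24 | 2296.5 | 2288.7 |
| 24–72 | 3846.9 | 3779.9 |
| 72–144 | 3345.3 | 3217.5 |
| 144–216 | 1672.6 | 1608.7 |
| 216–312 | 1038.4 | 970.3 |
| Tail | 638.4 | 638.4 |
| **AUC** | **13,204.6** | **12,870.0** |

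- AUC: 13,204.6/12,870.0 = +2.60%. CL: 12,870.0/13,204.6 = −2.53%.
- AUMC, standard tail: trapezoid 1,047,586 + 199,191 + 66,317 = 1,313,093 (rounded terms), against 1,336,858 exact (−1.78%). The straight lines understate t × C on the gaps up to 216 h and slightly overstate it on the last.
- MRT: 1,313,093/13,204.6 = 99.4 h against 103.9 h, −4.27%. Vss varies as AUMC/AUC²: 0.9822/1.0260² = 0.933, −6.69%.

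**Across the half-life range (linear rule, standard tail)**

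| Half-life | AUC | CL | MRT | Vss |
|---|---|---|---|---|
| 72 h | +2.6% | −2.5% | −4.3% | −6.7% |
| 96 h | +1.6% | −1.5% | −2.9% | −4.4% |
| 120 h | +1.0% | −1.0% | −2.0% | −3.0% |

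Linear-up/log-down gives 0.0% throughout.

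**Tail as printed.** C_last × t_last / K² has units of concentration × time³, whereas the trapezoid term has concentration × time². At 72 h it equals 20,690,770. MRT = (1,047,586 + 20,690,770)/13,204.6 = 1646 h against 104 h (+1485%), and Vss is +1445%. At 120 h, MRT is 8912 h against 173 h. With the log rule and this tail, MRT at 72 h is still 1691 h (+1528%).

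**Bi-exponential curves** (assumed: 30% or 40% fast fraction, fast half-life 12 or 20 h, terminal half-life 72 or 96 h, K from the last three points, standard tail; eight combinations):
- Linear: AUC +2.5% (30%, 20 h, 96 h) to +4.6% (40%, 12 h, 72 h); Vss −6.3% to −10.1%.
- Linear-up/log-down: AUC +0.6% to +1.3%; Vss −1.0% to −2.0%.

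**Trailing zero.** If the 312 h value at a 72 h half-life is set to 0 and integrated, AUC is −4.7% with the linear rule and −6.7% with linear-up/log-down. If integration stops at the last positive value (216 h), the figures are +2.1% and 0.0%.

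**Day 5 read as 96 h** (SAP 11 list, half-life 72 h, linear rule, standard tail): AUC +2.9%, MRT −5.3%, Vss −8.0%.

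**The case against.** The strongest case against is that the linear rule is openly prespecified, the PK analysis is secondary and descriptive, and nothing turns on a 1% to 3% shift. The interim PK analysis cannot alter the trial (Protocol 9.8), the dose formula uses the FORMA-01 recovery, and recovery, C_max, T_max and half-life do not use AUC. If the adult study used the linear rule, a switch could harm comparability. All of this stands and limits the weight of the point. It does not make the choice a matter of taste, because the alternative was closer to the truth on every curve tested that stayed positive.

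Four stronger readings are tempting, but the documents do not support them.
- *The plan as written understates MRT and Vss.* Only with the standard AUMC tail, or if the software's built-in AUMC is used. The SAP names the software but does not say that its AUMC overrides the printed formula, and under that formula both parameters are grossly overstated.
- *The log rule removes the bias.* That is exact only for a mono-exponential decline, which the log rule integrates without error by construction. The SAP expressly does not presume that shape.
- *The error has the same sign in every child.* Not where a final value is set to 0 and integrated: the AUC error then turns negative. The documents give no limit of quantification, so how often this would happen is unknown.
- *The bias rivals the sampling error.* With an assumed between-child CV of 30%, the standard error at n = 12 is 30%/√12 = 8.7%. The AUC bias is then about 0.1 to 0.3 standard errors. Vss reaches 6.7/8.7 = 0.77 only at the shortest half-life; at 120 h it is 3.0/8.7 = 0.35.

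The age-group effect is also modest. Even half-lives of 72 h and 120 h would shift the AUC comparison by only 2.6 − 1.0 = 1.6 percentage points.

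**Conclusion.** The concern holds as a minor, correctable flaw of method. For a mono-exponential decline with a half-life of 5 to 3 days, the linear rule on the protocol's times overstates AUC by 1.0% to 2.6% and understates CL by 1.0% to 2.5%, whatever the AUMC tail. For the assumed bi-exponential curves the AUC bias is larger, about 2.5% to 4.6%. The figures for MRT (−2.0% to −4.3%) and Vss (−3.0% to −6.7%) apply only once the AUMC tail is in standard form. As printed, the tail is the larger error, and changing the trapezoid alone would repair neither parameter.

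The sizes rest on noise-free curves, on all values used being positive, and on a background half-life for normal physiology rather than a design value for these children.

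**What to change.** Make one edit to the parameter table in SAP section 11:
1. Compute AUC and AUMC by linear-up/log-down: the log trapezoid where concentrations fall and both are positive, the linear trapezoid otherwise.
2. Replace the AUMC tail by C_last·t_last/K + C_last/K².
3. Define C_last as the last positive concentration, so that trailing values set to 0 are not integrated.
4. Reconcile the Day 5 entry in SAP 11 with Day 4 (72 h) in Protocol 6.1.2 and SAP 4.3.2.

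This removes the bias for a mono-exponential decline. In the bi-exponential checks on protocol times it leaves about +1% in AUC and −1% to −2% in Vss. The cost is a calculation setting in the PK software and a few lines of SAP text, with no added samples, visits or patients. The one drawback is possible loss of comparability with the adult study, whose integration rule the documents do not give. A supplementary linear-rule AUC line covers that.
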